5.3.2 Visit Windows for Safety Analyses

The date of all visits after the screening visit and the Week 1 (baseline) visit will be arranged within a time window of ± 1 day.

If an observation is missing at a specific scheduled visit, the value at that visit will be set to missing.

Visit recorded on CRF will be used as Analysis visit except Baseline visit.

5.3.3 Unscheduled Visit

Data collected as unscheduled visits will not be used for the tables but presented in the listing and subject data plot.

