4.7.2 Observation and Measurement

The trial procedures and evaluations at each visit are described below. For a summary of the scheduled visits and the trial procedures and evaluations at each visit, refer to Appendix 1 “Trial Schedule.” Unscheduled visits may be requested for subjects to ensure their safety if necessary.

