5.3 Safety Data Handling

5.3.1 Definition of Baseline

Baseline evaluations will be those collected (non-missing) closest to and prior to the first study drug infusion, which will be conducted –within 21 days of Week 1. For both GTI1401 and GTI1401-OLE, the baseline is the baseline visit at Week 1 in GTI1401 study.

For Pulmonary Function Tests

Values collected at “PRE-BRONCHODILATOR” time-point in screening visit will be defined as baseline for “PRE-BRONCHODILATOR”. Also values collected at “POST-BRONCHODILATOR” time-point in screening visit will be defined as baseline for “POST-BRONCHODILATOR”.

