11.2 Laboratory Tests

11.2.1 Summary Table of Laboratory Test

Population	:	Safety population
Contents	:	Summary statistics for original value and change from Baseline will be provided The analysis variables are defined in appendix for laboratory parameter. For Laboratory results, a data listing will be provided.
Analysis Visit for 1401	:	Baseline, Week 5 , Week 9
Analysis Visit for 1401- OLE	:	Baseline, Ext Week 26, Ext Week 52

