11.2.2 Summary Shift Table of Laboratory Test (Low, Normal and High)

11.2.3 Summary Shift Table of Laboratory Test (Normal and Abnormal)

Population	:	Safety population
Contents	:	Shift tables for laboratory test with normal range will be provided. The analysis variables are defined in appendix for laboratory parameter..
Analysis Visit for	:	Baseline, Week 5 , Week 9

1401		
Analysis Visit for 1401- OLE	:	Baseline, Ext Week 26, Ext Week 52

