11.3 Vital Signs

11.3.1 Summary Table of Vital Signs		
Population	:	Safety population
Contents	:	Summary statistics for original value and change from Baseline will be provided. The analysis variables are displayed in Table C. For vital signs results, a data listing will be provided.
Analysis Visit for 1401	:	Week 1 prior to Infusion (Baseline) and Week 1 (After completion of infusion), Week 2 ~ Week 8 (Prior to infusion / After completion of infusion)
Analysis Visit for 1401- OLE	:	Week 1 prior to Infusion (Baseline), Ext Week 1 ~ Ext Week 52 (Prior to infusion / After completion of infusion)

Table C:

Contents	Digits to be displayed
Pulse rate [BEATS/MIN]	Integer
Systolic blood pressure [mmHg] Diastolic blood pressure [mmHg]	Integer
Body temperature [C]	1 decimal place
Respiratory rate [breaths per minute]	Integer

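### Abnormal laboratory or vital-sign values seen only at an unscheduled visit are absent from the summary and shift tables, and no worst-post-baseline row recovers them

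*SAP*

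**What the plan says.** SAP 5.3.3 sets one rule for all off-schedule data: "Data collected as unscheduled visits will not be used for the tables but presented in the listing and subject data plot". It makes no exception for safety measurements. The only purpose the protocol gives for such visits is in 4.7.2: "Unscheduled visits may be requested for subjects to ensure their safety if necessary".

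SAP 5.3.2 governs how a record is assigned to a visit. It says "Visit recorded on CRF will be used as Analysis visit except Baseline visit", and also "If an observation is missing at a specific scheduled visit, the value at that visit will be set to missing".

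For GTI1401, SAP 11.2.1 gives the laboratory analysis visits as "Baseline, Week 5 , Week 9". Sections 11.2.2 and 11.2.3 use the same visits and say "Shift tables for laboratory test with normal range will be provided". For the extension, all three sections give Baseline, Ext Week 26 and Ext Week 52. The vital-sign summary in 11.3.1 covers Week 1 before and after infusion, then "Week 2 ~ Week 8 (Prior to infusion / After completion of infusion". No vital-sign shift table is planned.

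On baseline, SAP 5.3.1 says "Baseline evaluations will be those collected (non-missing) closest to and prior to the first study drug infusion", and then names the Week 1 visit of GTI1401 as the baseline for both studies.

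**The concern.** Safety is the primary objective of both studies, and the protocol synopsis includes abnormal changes in laboratory values and vital signs in the safety evaluation. An unscheduled visit called for safety is a likely place to find such a change, yet the rule keeps its measurements out of the tables. A laboratory shift table exists to show whether subjects moved out of the normal range. Under this rule it can show no shift for a parameter when the study file holds one.

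SAP section 1 says the planned analyses will go into regulatory submissions and possibly manuscripts. A reader of those may see the tables without the listings.

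**Working it through.** The plan states no figure to reproduce. The check follows an unscheduled value through the rules and table shells, then does simple counting.

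**1. Can the value enter under a scheduled label?** No. SAP 5.3.2 uses the visit recorded on the CRF, so an unscheduled record is not moved to a nearby scheduled visit. A missing scheduled value stays missing, so an unscheduled repeat cannot replace it. The only stated exception is Baseline.

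**2. Does any laboratory or vital-sign table have a row that is not tied to a visit?** No.

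| Table | Post-baseline rows, GTI1401 | Post-baseline rows, extension | Worst-value row |
|---|---|---|---|
| 11.2.1 laboratory summary | Weeks 5, 9 | Ext Weeks 26, 52 | none |
| 11.2.2 shift, low/normal/high | Weeks 5, 9 | Ext Weeks 26, 52 | none |
| 11.2.3 shift, normal/abnormal | Weeks 5, 9 | Ext Weeks 26, 52 | none |
| 11.3.1 vital-sign summary | Week 1 after infusion; Weeks 2 to 8 before and after | Ext Weeks 1 to 52, before and after | none |

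The Layout Plan shells agree, except that the vital-sign shell runs on to Week 9. SAP 5.3.4 says Week 12 data go into the safety tables, but 11.2.1 to 11.2.3 have no Week 12 row. If one were added, subjects not entering the extension would gain one more scheduled point, and the rule for unscheduled values would be unchanged.

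**3. How long are the gaps between tabulated laboratory points?**
- GTI1401: 5 − 1 = 4 weeks, then 9 − 5 = 4 weeks.
- Extension: SAP 4.1 makes Week 9 the first extension week. The gaps are 26 − 1 = 25 weeks, then 52 − 26 = 26 weeks. SAP Appendix 2 schedules hematology, chemistry and urinalysis only at Ext Weeks 26 and 52.

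An abnormality that arises and resolves within a gap can be measured only at an unscheduled visit.

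**4. What does the shift table then show?** Suppose one subject is normal at baseline and at both scheduled visits, and abnormal at one unscheduled visit between them. Let N be the number of subjects. Protocol 8.2 and SAP 5.4 give a minimum of 3; the values 4 and 5 are assumptions.

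| N | Subjects with a shift, as planned | Subjects with a shift, unscheduled value counted | Share |
|---|---|---|---|
| 3 | 0 | 1 | 1/3 = 33.3% |
| 4 (assumed) | 0 | 1 | 1/4 = 25.0% |
| 5 (assumed) | 0 | 1 | 1/5 = 20.0% |

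The laboratory shift shells print counts without percentages, so the visible difference is 0 against 1. The share is shown only for scale.

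**5. Are the substitutes named in 5.3.3 available?** The listing is. The laboratory listing shell is sorted by collection date within subject and parameter, gives the normal range, and flags high and low values. It has no dedicated marker for unscheduled records. The subject data plot is not specified: the only figures in the Layout Plan index are the PK concentration curves, 10.1.3 and 10.1.4.

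**The case against.** The strongest reply is that nothing clinically relevant goes uncounted. Protocol 5.3.7 says a laboratory abnormality that leads to withdrawal, needs treatment, causes apparent clinical manifestations or is judged relevant by the investigator should be reported as an adverse event. The adverse event tables in SAP 11.1 are not by visit and do not separate treatment from follow-up, so such an event would be counted there. Every value is also listed, and listings for about three subjects can be read in full. Finally, the rule excludes by visit label, not by result or trigger, and keeping irregular repeats out of by-visit means is a legitimate descriptive choice.

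Most of this stands. It limits the effect to measured values in the laboratory and vital-sign tables, and it is a good reason to leave the by-visit rows alone. It does not explain why a shift table should lack any row that reflects all post-baseline results. The adverse event route depends partly on the investigator's judgement and records an event, not a shift.

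A reader might infer three stronger things that the documents do not support:

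- **That the safety tables as a whole are biased towards normal.** The adverse event tables are not, provided 5.3.3 is not applied to them. Read literally, 5.3.3 could cover adverse events noted at an unscheduled visit, but SAP 11.1 counts every event from the first infusion to the final visit.
- **That 5.3.3 and 5.3.1 conflict outright on baseline.** SAP 5.3.2 exempts Baseline from the CRF visit label, 5.3.1 names Week 1, and Week 1 laboratory samples and vital signs are already scheduled before the infusion. The ambiguity needs an unscheduled pre-infusion repeat or a missing Week 1 value, and one clarifying sentence removes it.
- **That the gap is equally serious for vital signs.** These are tabulated before and after each infusion with a minimum and maximum per time point, and there is no shift table to mislead.

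**Conclusion.** The point holds in limited form. By the stated rule, a laboratory or vital-sign abnormality measured only at an unscheduled visit does not appear in tables 11.2.1 to 11.2.3 or 11.3.1. At the minimum of 3 subjects, one such subject makes a laboratory shift table count 0 instead of 1; at an assumed 4 or 5 subjects the count is likewise 0 instead of 1.

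This assumes that an unscheduled visit with laboratory or vital-sign measurements takes place, that the subject's tabulated scheduled values are normal, and that the CRF labels the visit as unscheduled. The documents do not say how often this will happen, so the table shows what one case does, not an expected rate.

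No data are lost and adverse event counting is not shown to be affected. The laboratory gap is longer in the extension, at 25 to 26 weeks between tabulated points against 4 weeks in GTI1401. The change is worth making because it is cheap and concerns the primary objective.

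**What to change.** 1. Keep the by-visit rows in 11.2.1 to 11.2.3 and 11.3.1 as they are.
2. Add a block to 11.2.2 and 11.2.3, for GTI1401 and the extension, for the worst post-baseline result over scheduled and unscheduled tests. In 11.2.2 abnormality runs in two directions, so define worst separately for low and high.
3. Add each subject's post-baseline minimum and maximum, unscheduled values included, to 11.3.1.
4. State in 5.3.3 that the rule applies only to by-visit measurement rows, and not to the adverse event tables or to baseline selection under 5.3.1.
5. Add the subject data plot to the Layout Plan, or delete the reference to it.

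The cost is one extra block per table from data already collected, with no protocol change. There is one statistical drawback: a worst-value row favours abnormal readings in subjects who are tested more often. The block should therefore be labelled as including unscheduled tests and read beside the by-visit rows, not in place of them.

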5.3.4 Follow-Up/End of Study Visit

30 days [4 weeks] after the completion of the last Alpha-1 MP infusion (Week 8) and 3 weeks after the Week 9 Visit, those subjects who do not participate in Study GTI1401-OLE will go to the clinic to complete a Follow-Up/End of Study Visit (Week 12). The Week 12 Visit should be scheduled at the protocol-specified study week relative to the date of the Week 1 (Baseline) Visit ± 1 day. The data collected during Follow-Up/End of Study Visit (Week 12) are included in Table and Listing for Safety Analysis and Concomitant Medication.

5.4 Sample Size

The targeted sample size is at least 3 subjects. Sample size was chosen based on clinical considerations and the number of available Japanese patients with AATD, not on a formal sample size calculation.

5.5 Rounding

In listings, data will be presented with the same precision as the original data; at the output creation stage, derived data will be rounded for presentation purposes.

For all summaries, the standard deviation will be presented to two decimal place greater than the original data, the mean and median will be presented to one decimal place greater than the original data and the minimum and maximum will be presented to the same number of decimal places as the original data.

For calculation of the proportion, one decimal place will be presented.

The rounding will be performed to the closest integer/first decimal using the common mid-point between the two consecutive values (e.g. 5.0 to 5.4 will be rounded to an integer of 5, and 5.5 to 5.9 will be rounded to an integer of 6)

Analysis Populations

- The All subjects screened will include all subjects during screening evaluations.
- The Safety population will include all subjects who receive any amount of Alpha-1 MP.
- The PK population (GTI1401 only) will include all subjects who receive Alpha-1 MP dose and have sufficient samples to calculate the PK parameters.

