8.1.2 Descriptive Statistics

Demographic and baseline characteristics, safety variables, and alpha₁-PI levels will be summarized using the safety population. For continuous variables, mean, standard deviation, median, minimum, and maximum will be provided. For categorical/qualitative data, absolute and relative frequency counts will be provided.

All subject data will be presented in data listings.

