4.1 Study Design and Plan

GTI1401 study is a multi-center, open-label, trial to evaluate the safety and PK of weekly IV infusions of 60 mg/kg Alpha-1 MP in Japanese subjects with AATD. At least three adult subjects will be enrolled in the study. The study consists of an up to three-week Screening Period, and an eight-week open-label Treatment Period including a one-week PK Assessment Period after the last infusion. At the Week 9 visit when the PK evaluation period is completed, subjects will be asked whether they would like to participate in an extension trial (GTI1401-OLE). For subjects not intending to participate in the extension trial, the date of follow-up/study completion visit (30 days [4 weeks] after the last dose of the investigational drug) will be arranged. The total duration of study participation for subjects who complete the study will be up to 14 weeks.

After providing informed consent at the Screening Visit, subjects will be evaluated for study eligibility during the Screening Period (up to three weeks); for study inclusion and exclusion criteria. Eligible subjects will enter the eight-week Treatment Period to receive a total of eight weekly IV infusions of 60 mg/kg Alpha-1 MP; subjects will receive their first infusion of Alpha-1 MP at the Week 1 (Baseline) Visit. During the Treatment Period, weekly infusions of Alpha-1 MP will be performed at the study site during scheduled study visits at Weeks 1 (Baseline), 2, 3, 4, 5, 6, 7, and 8. Subjects will receive their last infusion of Alpha-1 MP at the Week 8 Visit and will then enter the one-week

PK Assessment Period. During the PK Assessment Period, subjects have a last PK blood sampling study visit at Week 9. A Follow-Up/Final Visit (30 days [4 weeks] post last study drug infusion) will occur for subjects who will not participate in Study GTI1401-OLE.

[figure not shown]
All subjects will have a blood sample collected at Weeks 1 (Baseline), 7, and 8 (prior to the infusion of Alpha-1 MP) and Week 9 which will be used for the measurement of trough alpha₁-PI levels.

Blood samples for PK parameters will be collected beginning at Week 8 and the collection of blood samples will extend into Week 9. The pre-infusion serial PK sample at Week 8 and the last serial PK sample (7 days after the Week 8 infusion) at Week 9 will also serve as trough blood samples for Weeks 8 and 9. The specific timing of all 10 serial blood samples includes:

- Immediately prior to infusion

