4.2 Study Variables

No efficacy variables will be assessed for the studies. The variables to be assessed for GTI1401 and GTI1401-OLE studies are as follows:

- Adverse events, ADRs, serious AEs (SAEs), and discontinuations due to AEs or SAEs
- Vital signs (heart rate, blood pressure, respiratory rate, and temperature)
- COPD exacerbations
- Pulmonary function tests :
 - Forced Expiratory Volume in 1 second (FEV₁)
 - Forced Vital Capacity (FVC)
- Clinical laboratory parameters:
 - Chemistry
 - Hematology
 - Urinalysis
- Alpha₁-PI trough level
- PK parameters (GTI1401 study only):
 - AUC_{0-7 days}
 - C_{max}
 - t_{max}

- $t_{1/2}$
- CT scan (densitometry)

5 General Statistical Considerations

All analyses will be conducted using SAS Version 9.3 or higher.

Pharmacokinetic evaluations, descriptive statistical analysis of concentrations and PK parameters according to non-compartmental standard methods, as well as graphical representation of concentrations will be performed using the computer program Pharsight Phoenix WinNonlin (Version 6.1 or higher).

Unless otherwise specified, the results from GTI1401 and GTI1401-OLE will be presented separately.

Unless otherwise noted, for continuous variables, descriptive statistics will include the number of non-missing values, mean, standard deviation, median, minimum and maximum. For categorical variables, descriptive statistics will include counts and percentages per category.

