10.1.1 Summary Table of Alpha₁-PI Concentrations

Population	:	PK population
Contents	:	Alpha ₁ -PI concentrations will be summarized. The summaries will include n, mean (SD), coefficient of variation (%CV) (=SD/Arithmetic mean), median, minimum, maximum as well as geometric mean.
Digit	:	2 decimal places will be displayed for summary table of alpha ₁ -PI Concentrations.
Analysis	:	
 Immediately before the intravenous infusion

visit	
 • Immediately after infusion completion (after sodium chloride [NaCl] flush) (0 hour) • 15 minutes after infusion completion • 2 hours after infusion completion • 4 hours after infusion completion • 8 hours after infusion completion • 24±4 hours (1 day after infusion completion) • 48±4 hours (2 days after infusion completion) • 120 hours ± 1 day (5 days after infusion completion) • 168 hours ± 1 day (7 days after infusion completion) (Week 9 Visit) 
Serum concentrations of alpha₁-PI determined by content assay will be presented in a listing by subject, study week, and scheduled or nominal time point.
 
This data listing will provide details of all planned plasma collection time points (scheduled and nominal times as specified in Section 12.1), actual collection date and clock times and elapsed times from the start of the study drug infusion, as well as alpha₁-PI concentrations. Samples excluded from PK analysis will be flagged.
 
The date/clock time for the start and completion of study drug infusion, the actual volume infused, and the actual dose infused (mg/kg) at Week 8 (PK assessment visit) will be presented in a separate listing.

-------	--

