10.1.2 Summary Table of Trough (pre-infusion) Levels (C_{min}) and mean C_{min}	
Population	: PK population
Contents	
This table include following contents.
 
 • Summary of trough (pre-infusion) levels (C_{min}) and mean C_{min} at steady state by week number (for C_{min}). 
Mean C_{min} calculated by the trough levels from weeks 7, 8, and 9 (exclude Week 1).
 
 • Number and Proportion with mean C_{min} of alpha₁-PI Concentration \geq 50 mg/dL (=11.3 μM nearly equal to 11μM which is defined in ATS/ERS statement in 2003). A conversion factor of 0.226 based on the protein only molecular weight of 44.3 KDa for alpha₁-PI is used for converting mg/dL to μM (i.e., 1 mg/dL alpha₁-PI = 0.226 μM). 
No data imputations will be involved in the above concentration data listings, summaries, or figures.
 
Trough (pre-infusion) levels (C_{min}) and mean C_{min} at steady state will

		be listed
Digit	:	2 decimal places will be displayed for summary table of C_{\min} .
Analysis visit (only C_{\min})	:	Week 1, Week 7, Week 8 and Week 9, *mean C_{\min} = Average of C_{\min} of each patient measured at Week 7, Week 8 and Week 9 (exclude Week 1)

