10.1 PK Analysis (GTI1401 only)
10.1.1 Summary Table of Alpha1-PI Concentrations

PK population

Alpha1-PI concentrations [mg/dL]

Time Points

Statistics

Immediately before the intravenous infusion

N	xx
Mean(S.D.)	xx.x (xx x)
%CV	xx.x
Median	xx.x
Min , Max	xx , xx
Geometric mean	xx.x

Immediately after the intravenous infusion (after flushing the infusion line with physiological saline) (at 0 hours)

N	xx
Mean(S.D.)	xx.x (xx x)
%CV	xx.x
Median	xx.x
Min , Max	xx , xx
Geometric mean	xx.x

15 minutes after completion of the intravenous infusion

N	xx
Mean(S.D.)	xx.x (xx x)
%CV	xx.x
Median	xx.x
Min , Max	xx , xx
Geometric mean	xx.x

...

GTI 1401
10 Exploratory Analysis

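### The protocol reports alpha1-PI levels in the Safety Population and lists all data; the SAP puts the trough table and every alpha1-PI listing on a loosely defined PK population and declares no change

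*SAP*

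**What the plan says.** **Protocol.** Section 8.1.1 defines one analysis set, the Safety Population (anyone given any amount of drug). Section 8.1.2 says of alpha1-PI that "PI levels will be summarized using the safety population", and adds: "All subject data will be presented in data listings". The trough level is the secondary objective (3.2); AUC, Cmax, tmax and t1/2 are exploratory (3.3). Section 6.2 (4) does not replace dosed subjects who discontinue, and 8.2 sets a target of at least 3 subjects.

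**SAP.** The analysis-population list that follows 5.5 adds a second set: "The PK population (GTI1401 only) will include all subjects who receive Alpha-1 MP dose and have sufficient samples to calculate the PK parameters". That set is named as the population for the concentration table (10.1.1) and the trough table (10.1.2). In the Layout Plan it also heads Listings 10.1.6, 10.1.7 and 10.1.8. The Cmin analysis visits in 10.1.2 are "Week 1, Week 7, Week 8 and Week 9". SAP 4.1 says that the Week 8 pre-infusion sample and the 7-day sample "will also serve as trough blood samples for Weeks 8 and 9". SAP 13 states that nothing has changed from the planned analysis.

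**The concern.** The protocol names the population for alpha1-PI levels, and the SAP uses another without saying so. Under the SAP, whether a secondary-endpoint value is reported can depend on whether the same subject later gave an adequate serial profile for exploratory parameters. A Week 7 trough needs no Week 8 to 9 profile to be valid.

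The listings matter as much as the table. If only the summary were restricted, a reader could still find the excluded values in a listing. Here the concentration listings carry the same restriction. Listing 6.3 would show that a subject was left out of the PK population and why, but it shows no concentrations. The demographic outputs (Table 8.1, Listing 8.2) give only the level at diagnosis. With a target of 3 subjects and no replacement, one subject is a large share of the data.

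**Working it through.** **1. Is the population difference real?**

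| Output | Protocol 8.1.2 | SAP |
|---|---|---|
| Trough summary, Table 10.1.2 | Safety | PK |
| Listings 10.1.6 to 10.1.8 | all subject data | PK |
| Concentration summary, Table 10.1.1 | Safety, if levels covers the serial profile | PK |
| AUC, Cmax, tmax, t1/2, Table 10.1.5 | no set named (8.1.3 leaves methods to the SAP) | PK |

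The first two rows are contradictions. The third depends on how the word levels is read. The fourth is ordinary SAP elaboration.

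**2. What does membership require?** The definition leaves three things open.
- *How many samples.* The only stated minimum is three time points for the elimination rate constant (Calculation of PK Parameters, t1/2). It is not tied to membership.
- *All parameters or any one.*
- *Whether Cmin counts.* SAP 4.2 lists the trough level separately from "PK parameters (GTI1401 study only", and 3.3 names four parameters without Cmin. The Calculation of PK Parameters section and Listing 10.1.9 include Cmin.

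The Cmin label is itself inconsistent. The Calculation section defines it from Weeks 7, 8 and 168 hours only. Section 10.1.2, the Table 10.1.2 shell and Listing 10.1.8 also label the Week 1 value Cmin.

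**3. Who drops out under each reading?**

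| Reading | Week 7 trough only, or Weeks 7 and 8 pre-dose only | Three troughs, too few points for t1/2 | Stops before Week 7 |
|---|---|---|---|
| All parameters, with or without Cmin | out | out | out |
| Any of AUC, Cmax, tmax, t1/2 | out | may stay (Cmax is observed) | out |
| Any, Cmin counted | stays | stays | out, unless the Week 1 value qualifies as Cmin |

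Counting Cmin therefore helps only under the any-one rule. Under the all-parameters rule it adds a requirement.

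**4. Size, given one excluded subject.** The plan has no figure to reproduce, because the sample size is not a formal calculation. Let k be the troughs obtained in the excluded subject, and let the other n − 1 subjects have all three. The share unreported is k / (3(n − 1) + k).

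| k | n = 3 | n = 4 | n = 5 |
|---|---|---|---|
| 1 | 1/7 = 14.3% | 1/10 = 10.0% | 1/13 = 7.7% |
| 2 | 2/8 = 25.0% | 2/11 = 18.2% | 2/14 = 14.3% |
| 3 | 3/9 = 33.3% | 3/12 = 25.0% | 3/15 = 20.0% |

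For a subject who stops before Week 7 and is excluded, the share of Week 1 levels unreported is 1/n: 33.3%, 25.0% and 20.0%. The value n = 3 is the documents' minimum; n = 4 and n = 5 are assumed, to show the range.

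**The case against.** Four arguments favour the SAP.

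- *The protocol defers to the SAP.* Sections 8.1 and 8.1.3 leave data handling and PK calculation to it. That supports a PK set for AUC, Cmax, tmax and t1/2. It does not reach a variable whose population 8.1.2 names.
- *Levels may mean troughs only.* The protocol's endpoint list separates the trough level from PK parameters, and 8.1.3 treats concentration data under PK. On that view the serial concentration table may properly sit on a PK set. This stands, so Table 10.1.1 is a weaker case than Table 10.1.2. The sentence requiring all subject data to be listed still covers the listings.
- *Exclusions are disclosed.* Listing 6.3 gives the reason, and SAP 10.1.1 adds: "Samples excluded from PK analysis will be flagged". But that flag sits in listings restricted to the PK population, so it cannot show the values of a subject outside that set.
- *The study is small and descriptive.* It has no hypothesis test, and its primary objective is safety. This limits the seriousness of the point but does not remove the contradiction.

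Two stronger inferences are tempting. A reader might conclude that a subject who stops before Week 7 is excluded on every reading. The documents do not establish that, because parts of the SAP call the Week 1 value Cmin. A reader might also conclude that the population choice inflates the proportion above the trough threshold. That would need an assumption about the excluded subject's level, and the documents give no basis for one.

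**Conclusion.** The SAP contradicts Protocol 8.1.2 on the population for the trough summary and on listing all subject data, and SAP 13 does not declare it. The membership rule is too loose to tell who would be affected.

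The loss is conditional. It requires a dosed subject who has valid levels and falls outside the PK population. With one such subject at n = 3, between 14.3% and 33.3% of obtained steady-state troughs go unreported, assuming the other two subjects have all three. Alternatively, 33.3% of Week 1 levels go unreported for an excluded early stopper. If every dosed subject has a sufficient profile, the two populations coincide and nothing is lost. No direction of bias is claimed. The point should be corrected; it does not threaten the primary safety objective.

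**What to change.** 1. Set SAP 10.1.2, Table 10.1.2 and Listings 10.1.6 to 10.1.8 to the Safety Population, including every subject with a sample at the visit or time point. Listings 10.1.6 and 10.1.7 already have a column for marking exclusion from the PK analysis; use it there.
2. Keep the PK population for AUC, Cmax, tmax and t1/2 (Table 10.1.5), and state which of these must be calculable for membership.
3. For Table 10.1.1, either move it to the Safety Population together with Figures 10.1.3 and 10.1.4, or keep all three on the PK population and record this in SAP 13 as a departure from, or interpretation of, Protocol 8.1.2. The table and figures should move together, so that a partial profile does not enter the mean plot while missing from the individual plots.
4. As a secondary clarification, state whether Week 1 is a Cmin and whether mean Cmin needs all three troughs. Section 10.1.2 averages the values measured at Weeks 7, 8 and 9, while the Calculation section refers to three measurements. Either rule would reconcile them.

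The cost is SAP and shell wording, with no new data and no change in conduct. The downside is that n may differ between rows and between tables. The Table 10.1.2 shell already prints N for each visit.
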